5 TREATMENT OF SUBJECTS

5.1 Investigational product/treatment

The active intervention group will receive Lacprodan® OPN-10, as a food supplement. The placebo group will receive a supplement in which Lacprodan® OPN-10 is replaced by maltodextrin, but indistinguishable in appearance and taste.

5.2 Use of co-intervention / restrictions

Subjects will be instructed to maintain their habitual lifestyle. Regular use of food supplements can be part of such lifestyle, but any changes in dietary pattern during the study period should be discussed with the study staff first.

With respect to the test days the following restrictions need to be met:

- No alcohol consumption on the day prior to the visits
- On the visit days, the subjects visit the research facility after an overnight fast (no eating or drinking after 21.00h (except for water)

6 INVESTIGATIONAL PRODUCT

6.1 Name and description of investigational product(s)

Lacprodan® OPN-10 is an osteopontin (OPN)-based milk-derived protein product isolated from bovine whey and produced by commonly used ultrafiltration and ion exchange chromatography (IEC) processes in the whey industry to fractionate whey. The Lacprodan® OPN-10 batch used for this study has protein content of 79.6% based on conventional calculations (N*6.38) and 89.5% protein based on appropriate correction factors (N*7.17) included in calculations for this ingredient. OPN comprises > 99.5% of the total protein.

Lacprodan® OPN-10 is a proprietary food ingredient produced and sold by AFI containing OPN isolated from bovine whey processed under current Good Manufacturing Practices (cGMP). Further detailed information about the identity of the investigational product can be found in the notification of GRAS status for Lacprodan OPN-10 (Matulka 2017; EFSA NDA Panel 2022).

Table 1. Chemical composition of Lacprodan® OPN-10

Chemical composition (%)	Lacprodan® OPN-10
Protein (Nx6.38)	79.6
Protein (Nx7.17)	89.5
OPN of total protein	>99.5
Lactose	0.1

Fat	0.2
Ash	9.4
Calcium	2.49

Table 2. Main ingredient composition of the intervention products, per 1000 mg

Ingredient	Lacprodan® OPN-10 sachets	Placebo sachets		
Lacprodan OPN-10	1400 (<70kg) or 1800 mg (>70	0		
	kg) (~12,70 or 16,40% of total			
	weight)			
Of which OPN	~89% is OPN	0		
Maltodextrin	~78,00-82,00% (depends on	94,55 %		
	amount of OPN-10)			
Lemon flavour	2,10%	2,10%		
Sucralose	0,17%	0,17%		
Citric Acid Monohydrate	2,80%	2,80%		
Colour yellow	0,38%	0,38%		
Antifoam (for fast foam	0,04%	0%		
knockdown in protein shake)				

6.2 Summary of findings from non-clinical studies

Results from *in vitro* and *in vivo* safety evaluations have been published (Kvistgaard et al. 2014). In vitro genotoxicity tests conducted according to accepted guidelines at up to 5000 µg/plate OPN failed to induce genetic mutations in *Salmonella typhimurium* strains and *Escherichia coli* strain and did not induce chromosomal aberrations or cytotoxicity in human lymphocytes. Administration of an acute dose of Lacprodan® OPN-10 (2300 mg/kg body weight) to male and female mice did not induce chromosomal damage or mitotic apparatus damage to erythroblasts from bone marrow. Lacprodan® OPN-10 was evaluated in a 13-week oral toxicity study in which rats were fed diets containing 0.5%, 1.0% and 2.0% Lacprodan® OPN-10. No test-article-related clinical observations or toxicological effects on body or organ weights, food consumption, ophthalmic effects, locomotor activity, hematology, clinical chemistry, urinalysis, or pathology were identified. In a teratogenicity study, administration of Lacprodan® OPN-10 up to 2500 mg/kg bw/day via gavage to pregnant rats had no effect on dams or pups. The No Observed Adverse Effect Level (NOAEL) for Lacprodan® OPN-10 in the 13-week toxicity study was 2.0% of the diet (equivalent to 1208 mg/kg bw/day in male rats and 1272 mg/kg bw/day in female rats).

OPN has been closely associated with functions involving the immune response, including binding integrin receptors expressed on inflammatory cells (e.g., neutrophils, macrophages and mast cells), promoting chemotaxis or cell activation (especially as an important early regulator of Th1-mediated immunity) (Ashkar et al. 2000), and acting as an opsonin by enhancing phagocytosis in vitro through a novel (aXb2 integrin) OPN receptor (Schack et al. 2009). Nau et al. (Nau et al. 2000) found that OPN expression after infection by mycobacteria is inversely proportional to patient outcome; that is, "patients who do well after an infection by mycobacteria express high levels of OPN." Patients with

localized infection tended to have a higher OPN expression. The authors of the study concluded that "osteopontin expression correlates with an effective immune and inflammatory response when humans are challenged by a mycobacterial infection and that osteopontin contributes to human resistance against mycobacteria" (Nau, Chupp et al. 2000). Overall, there is no single known specific function of OPN. Experimental evidence indicates that OPN may have multiple, beneficial actions on different biological systems (Matulka 2017).

In young animals, bOPN has been shown to stimulate immune development in a similar way as endogenous OPN (Jiang & Lonnerdal 2020), and LPS-injected piglets tended to have a lower incidence of diarrhoea after bovine OPN intake (Ren, Hui et al. 2019). In a study in piglets, an increased response to influenza vaccination has been observed after bovine OPN administration (Donovan 2017).

6.3 Summary of findings from clinical studies

Clinical studies with OPN-10 have been performed in infants. Lacprodan® OPN-10 in dosages of 65 mg/L or 130 mg/L was shown to be well tolerated in infants (Lonnerdal, Kvistgaard et al. 2016). In the same study, it was shown that OPN downregulates inflammatory cytokines (TNF-α) in infants which had received infant milk formula with Lacprodan® OPN-10 when compared to infants who had received regular infant milk formula without Lacprodan® OPN-10 (West, Kvistgaard et al. 2017). All infants were vaccinated with a trivalent vaccine (diphtheria, pertussis, tetanus) at 4 months of age. The antibody titre (IgG) against tetanus was measured at 6 months of age (Lonnerdal, Kvistgaard et al. 2016). There was no significant difference between breastfed and formula-fed infants, but among the formula groups, the mid-dose group had fewer antibodies than the low-dose group. There were no statistically significant differences between the high-dose group and any of the other groups. It was shown that the infants which had received the infant formula with 130 mg/L Lacprodan® OPN-10 had increased T-cell proportions compared with infants which had received infant milk formula with a lower dosage (65 mg/L) or a control formula without Lacprodan® OPN-10 (West et al. 2017). Furthermore, monocyte proportions were higher in the infants receiving Lacprodan® OPN-10, when compared to the breast-fed reference group. Higher plasma levels of human OPN were observed in infants receiving infant milk formula with bovine Lacprodan® OPN-10 when compared to infants receiving a control formula (Jiang and Lonnerdal 2019), suggesting that bovine Lacprodan® OPN-10 promotes the synthesis or secretion of endogenous human OPN. They attributed this to small amounts of undigested bOPN being absorbed stimulating endogenous OPN production by similarities in the amino acid sequences. This is consistent with findings in animal studies with both young (Jiang, Prell et al. 2019) and adult (Ge, Lu et al 2013) mice.

Effects of Lacprodan OPN-10 in adults have not yet been studied.

6.4 Summary of known and potential risks and benefits

Recently, the EFSA Panel on Nutrition, Novel Foods and Food Allergens (NDA) published an opinion on bovine milk osteopontin as a novel food, in which they conclude that the currently available scientific data do not raise safety concerns (EFSA NDA Panel 2022).

In 2017, a GRAS notification (Matulka 2017) has been submitted to the FDA for the use of Lacprodan® OPN-10 in non-exempt cow's milk based infant formula and cow's milk based powdered beverages targeted for children 1-3 years of age, at an estimated upper consumption level of 39.5 mg/kg body weight/day. The GRAS status was based on the views of an independent Expert Panel. Standard safety evaluations have shown no indications for potential risk involved with consumption. Potential benefits in the general adult population have not been studied so far.

6.5 Description and justification of route of administration and dosage

The intervention product has been developed as a food supplement or nutritional ingredient. Therefore, the appropriate route of administration is by ingestion, supplementing the normal diet. The product will be supplied in two different dosages: 2.5 g/day for subjects weighing lower than 70 kg at screening, and a dose of 3,20 g/day for subjects weighing 70 kg or more at screening.

The estimated intake of OPN-10 in infants, based on 160 mg OPN-10/L infant formula, is 24.8 mg/kg BW/day for infants at the 50th percentile, and 39.5 mg/kg BW/day for infants at the 90th percentile. The influenza vaccination study in piglets (Donovan 2012) provided an intake of 50.4 mg/kg BW/day. No data are available from any study in adult human subjects. The selected dosages result in an intake of 50 mg per kg BW for subjects weighing 50 kg, and 35,6 mg/kg BW for subjects weighing 105 kg, which is at the high end of the regular intake in infants, via OPN-10 supplemented infant formula, but still within the safety range.

6.6 Dosages, dosage modifications and method of administration

OPN will be administered in the form of sachets. The individual dose is dependent on the body weight at screening, with a dose of 2.5g/day for subjects weighing lower than 70 kg at screening, and a dose of 3,20 g/day for subjects weighing 70 kg or more at screening. Each participant will consume 2 sachets of study product per day. The dosage will not be adjusted in case a weight change occurs during the study.

Table 3. Calculation of individual dose of OPN with 2 sachets per day

Weight of subject at screening (kg)	Daily intake (grams)	Amount per sachet	Actual dose (mg/kg BW)	
50	2,5	1,25	50,0	
55	2,5	1,25	45,5	
60	2,5	1,25	41,7	

65	2,5	1,25	38,5
70	3,2	1,6	45,7
75	3,2	1,6	42,7
80	3,2	1,6	40,0
85	3,2	1,6	37,6
90	3,2	1,6	35,6
95	3,2	1,6	33,7
100	3,2	1,6	32,0
105	3,2	1,6	30,5

The sachets will be taken in 2 servings per day: 1 sachet in the morning at breakfast, and 1 sachet in the evening at dinner. In case of a missed dose, subject can consume the missed sachets at a later timepoint on the same day.

6.7 Preparation and labelling of Investigational Product

Test and placebo products will be delivered to NIZO separately by the sponsor and will be stored at the recommended conditions.

On the label of the bulk package, the following information will be provided by the sponsor: Bulk packaging coming from sponsor

- Company name sponsor
- Project number of the study (xxx)
- Manufacturing batch number
- Number of carton boxes with 30 sachets
- Expiry date
- The text "for nutrition trial use only"

An example of the label of the bulk package is included in section D3 of this submission.

The products will be packaged in carton boxes. All boxes will contain 30 sachets. The sachets will be marked with one dot (.) for the sachets with a level of 1,25g/sachet and with two dots (..) for the sachets with a level of 1,6 g/sachet. Each carton box will be delivered to NIZO with the following information:

- Best before [date]
- Random 5-digit code (see section 8.2)
- Number of sachets

NIZO will add an additional label to the carton boxes with the following:

- Study name
- Subject number
- "To be used in study weeks: ..."
- The text "for nutrition trial use only" (in Dutch)

For the active treatment, 3 random 5-digit codes will be used; for the placebo treatment, 3 other random 5-digit codes will be used. Each carton box will be coded with one of the three applicable codes.

For each subject, 2-weekly packages will be prepared by NIZO. Labelling of these packages with the individual subject codes and weeks will be performed by NIZO. After arrival of the bulk package at NIZO, the NIZO study team will be responsible for labelling of the 2-weekly doses of the study products.

The label that will be used on the 2-weekly package for the subjects ('Voorbeeldetiket D3') will contain the following information:

- Study name and project number
- Subject number
- Best before [date]
- Random 5-digit code (see section 8.2)
- The text "for nutrition trial use only" (in Dutch)
- Information for use
- Information about storage conditions
- Contact details of the researcher

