8.2 Randomisation, blinding and treatment allocation

To ensure blinding of the NIZO study team, an independent person in the AFI study team will be responsible for assigning a random 5-digit number code to the products. The number code is printed on the label of each carton box. Per treatment 3 different, 5 digits, codes will be used. The NIZO and EBMR teams, laboratory personnel and participants will be unaware of the coding until all data analyses are finished and until after the blind data review meeting. Only in a case of emergency possibly related to treatment, the Principal Investigator can request the independent party to open a sealed de-blinding envelope containing information to check the type of treatment of (a) particular subject(s) without disclosure of the other treatments.

Allocation will be stratified for gender and age.

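### Delivering test and placebo to the NIZO team separately lets it group all six product codes, and so all 140 subjects, into two unnamed arms, which undercuts the blinding set up in section 8.2

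*Protocol*

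**What the plan says.** Section 8.2 of the protocol has an independent person at the sponsor give the products random 5-digit codes, and states the purpose: "To ensure blinding of the NIZO study team". The NIZO and EBMR teams, the laboratory staff and the participants are to stay unaware of the coding until the analyses and the blind data review are done. An emergency envelope is meant to reveal the treatment of a particular subject without revealing the others.

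Section 6.7 sets the number of codes: "For the active treatment, 3 random 5-digit codes will be used; for the placebo treatment, 3 other random 5-digit codes will be used". It also fixes the logistics:

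- Delivery: "Test and placebo products will be delivered to NIZO separately by the sponsor".
- The bulk label lists, among other items, "Manufacturing batch number" and an expiry date. It lists no treatment name.
- Codes are on the cartons on arrival: "Each carton box will be delivered to NIZO with the following information", a list that includes the 5-digit code and a best-before date.
- Handling: "After arrival of the bulk package at NIZO, the NIZO study team will be responsible for labelling of the 2-weekly doses".
- Link to subjects: "Labelling of these packages with the individual subject codes and weeks will be performed by NIZO".

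Neither section describes mixing the consignments, masking the batch number, or receipt by someone outside the blinded team.

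**The concern.** Using several codes per arm has one purpose: a person who sees the codes should not be able to tell which belong together. Section 6.7 delivers the codes already sorted by arm, to the team from which the sorting is to be withheld, and has that team tie the codes to subjects. This is a stated rule, not a detail left open for the analysis plan.

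At stake is mainly the blind data review, where the criteria for excluding subjects from the per-protocol population are applied (section 10). If anyone present can place subjects in group A or B, the meeting is no longer blind in the sense intended, and its exclusions can be challenged even if nobody acted on the knowledge. A second, conditional exposure is the cytokine, OPN and LBP assays, which section 8.1.2 places at NIZO.

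**Working it through.** **Inputs.** Six codes, three per arm (6.7, 8.2). 140 subjects, 70 per group (4.4, 11.2). Codes on the cartons on arrival, and subject numbers added by NIZO (6.7).

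**The plan's own figure.** The 140 comes from the sample size in 4.4. For 25% versus 50%, two-sided alpha 0.05 and power 0.80:

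n = [1.960 × √(2 × 0.375 × 0.625) + 0.842 × √(0.25 × 0.75 + 0.5 × 0.5)]² / 0.25² = (1.342 + 0.557)² / 0.0625 ≈ 57.7, so 58 per group, as stated.

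With 15% drop-out, 58 / 0.85 = 68.2, so 69, against 70 planned. The sample size is not in question; it only supplies the 140.

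**Step 1: codes arrive mixed.** Six codes split into two unnamed sets of three in C(6,3)/2 = 20/2 = 10 ways. With the arms named there are 20.

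**Step 2: codes arrive by arm.** Every code in one delivery belongs to one arm. One split remains, with two ways to name it.

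**Step 3: link to subjects.** NIZO attaches subject numbers to coded cartons, so the one split sorts 140 of 140 subjects into A and B.

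**Step 4: one emergency envelope.** Without the grouping, learning one subject's treatment gives the arm of that subject's code, about 140/6 = 23.3 subjects, and leaves C(5,2) = 10 arrangements of the other five codes. With the grouping it gives the arm of all 140. The 23 assumes that the codes are used equally and that each subject stays on one code; the protocol states neither.

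**Step 5: what the batch number adds.** Table 2 gives active and placebo different compositions, so no batch can span both arms. But the active product has two strengths, and the number of batches per arm is not given. Batch alone therefore gives clusters that are each pure for one arm, possibly more than two of them. The two-way split rests on separate delivery.

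**Step 6: where the grouping could act.**

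| Activity | Who, per protocol | Exposure |
|---|---|---|
| Packing and subject labels | NIZO study team (6.7) | direct |
| Blind data review | blind meeting; members not listed (10) | if the NIZO study team takes part |
| Cytokines, OPN, LBP | NIZO (8.1.2); laboratory staff listed apart from the team (8.2) | only if the grouping reaches them |
| Primary anti-HB ELISA | site not given (8.1.1) | no direct route shown |
| Visits, sachet counts | EBMR (3, 6.8) | not shown; EBMR does not receive bulk packs |

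**The case against.** The strongest reply is that much more could be inferred from section 6.7 than it supports. Most of that reply stands.

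- **Full unblinding.** A reader might infer that NIZO learns who is on active product. The bulk label names no treatment, and nothing says that NIZO could recognise a batch number. Only an unnamed grouping is exposed.
- **Separate consignments.** The text says *separately* but gives no dates or number of shipments, and later speaks of the bulk package in the singular. The reading used here is the ordinary one, but it is a reading.
- **Batch number as a key.** By itself it may give more than two clusters, as shown above.
- **Bias in outcomes.** The primary endpoint is an ELISA titre against a cut-off, at a site not said to be NIZO. Samples carry the study code, entry number and visit code, not the product code (12.1), so laboratory staff would have to be told the grouping. Per-protocol criteria are to be defined in the analysis plan; the review applies them.
- **Grouping is needed anyway.** An analysis by arm cannot be completed without grouping subjects, so section 8.2 may tolerate unnamed groups at that stage.

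The last point concerns timing. Grouping for the analysis can follow the blind data review, whereas section 6.7 releases it before the first subject is supplied. Three codes per arm would serve little purpose if the grouping were meant to be known from the start. Nor is it a safeguard to hope that no one notices which pack a code came from.

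**Conclusion.** The point holds in limited form. On the ordinary reading of *separately*, section 6.7 lets the people who unpack reduce ten possible splits of the codes to one and place all 140 subjects in group A or B. That weakens the safeguard in section 8.2. It does not by itself show which group is active. One opened envelope would, however, settle the arm of 140 subjects instead of about 23. Another clue could do the same, for example a group difference in bovine OPN if it is measurable in adult plasma, for which the protocol has no adult data.

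The conclusion should not be stretched to a biased primary result: the documents show no direct route to that endpoint, and they give nothing from which the size of any bias could be calculated. The practical weight lies with the blind data review and, if the grouping spreads to laboratory staff, with the secondary assays run at NIZO. The matter should be corrected before product is shipped, because a grouping once seen cannot be withdrawn.

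**What to change.** Rewrite section 6.7 as follows:

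1. Delete *separately*. The independent code-holder at the sponsor mixes coded cartons of both arms within each dose level before shipment. This requires placebo cartons to carry the same dot marks as active ones; section 6.7 describes the dots only by amount per sachet and should say so.
2. Use a neutral bulk label with no batch number or expiry date specific to an arm.
3. Use one common best-before date on the bulk label, the cartons and the 2-weekly packages. Changing only the bulk label would leave a clue on the cartons if the dates differ by arm.
4. Keep the batch-to-code list sealed with the code-holder, so that traceability and NIZO's accountability duty under section 6.8 are preserved.

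Having someone outside the blinded NIZO team receive and label the product would also serve.

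The cost is one extra handling step before shipment and a short change of wording. The drawback is that tracing a batch goes through the sealed list instead of the outer label. Sample size, visits and analyses are unaffected.

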6.8 Investigational product accountability

The sponsor is responsible for transportation of products to NIZO study location by means of a courier. NIZO is responsible for overall IP accountability and storage at the recommended conditions. EB Medical Research is responsible for providing subjects at Visits 2, 3, 4, 5 and 6 with sufficient study product until the next visit, according to the randomization schedule. EB Medical Research is responsible for subject IP accountability.

At each of the visits 2 to 6, each subject will receive one or more carton boxes, with at least the number of sachets required until the next visit, and instruction on the number of sachets to take each day. At each of the visits 3 to 7, subjects have return the empty carton boxes and the carton boxes with the unused sachets of the previous study weeks. The leftover sachets will be counted by the EBMR study team to check compliance. At the end of the study, leftover sachets will be returned to the sponsor.

7 NON-INVESTIGATIONAL PRODUCT

7.1 Name and description of non-investigational product

The non-investigational product in this study is the registered Engerix-B® vaccine. For details on the product composition we refer to the Summary of Product Characteristics (SPC), h17316 smpc.pdf (geneesmiddeleninformatiebank.nl).

7.2 Summary of findings from non-clinical studies

See SPC, h17316 smpc.pdf (geneesmiddeleninformatiebank.nl)

7.3 Summary of findings from clinical studies

Engerix-B induces the development of specific humoral antibodies to hepatitis B antigens. Anti-HB antibodies \geq 10 IE/I provide protection against infection with hepatitis B virus.

7.4 Summary of known and potential risks and benefits

The safety profile for Engerix-B is described in the SPC. Side effects that are reported to occur often or very often are: loss of appetite, irritability, headache, gastrointestinal symptoms (e.g., nausea, vomiting, diarrhea, abdominal pain), pain and redness at the injection site, fatigue, fever, malaise. Less common side effects include dizziness, myalgia, and influenza-like symptoms.

The benefit of the vaccination is the protection against hepatitis B virus infection. However, due to the accelerated schedule, seroprotection will be achieved for about 75% of the participants (h17316 smpc.pdf (geneesmiddeleninformatiebank.nl).

